9.2. Exposure and Compliance

The duration of study drug exposure is defined as the number of days on treatment analysis group from the first dose of study drug until the last dose of study drug (last dose - first dose + 1). Study drug exposure is summarized by descriptive statistics. Summaries include the total dose (mg) received (based on the number of pills returned), study drug compliance, the number and percentage of patients receiving study drug by scheduled dispense visit (reference visit window table), and duration (days) of exposure during the study treatment period.

In addition, a summary of the number and percentage of patients on bardoxolone methyl by visit and dose (5 mg, 10 mg) is generated.

Total number of doses dispensed and total dose (mg) dispensed are calculated from total number of kits (bottles) recorded on the Study Drug Dispensation eCRF. Total number of doses received are calculated from information on the eCRF of Study Drug Return and Study Drug Dispensation, as the total number of doses dispensed – total number of doses returned. Study drug compliance (%) is calculated as $100 \times \text{total number of doses received} / \text{total number of doses dispensed}$. For patients who remain on study treatment at the time of an interim or final data cut, the last kit dispensed date is considered the date of last dose.

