#### **9.10.10. Study Drug Dispensation and Collection**

Study drug will be dispensed to the patient and collected from the patient as indicated in [Table 3](#). The patient will be dispensed 1 or more treatment kits at Day 1, Week 4, Week 24, and every 24 weeks thereafter for the duration of the study. Dispensed treatment kits from each visit should be returned to the site for collection at the subsequent visit.

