### 10.2. Study Drug Packaging and Labeling

The study drug will be supplied in tamper-evident kits containing one 30-cc (5-mg capsules, 30 count), one 60-cc (5-mg capsules, 90 count), or one 100-cc (10-mg capsules, 90 count) high-density polyethylene bottle. Each bottle will utilize foil induction-seal liners and a child-resistant closure. Each bottle of study drug will contain 30 or 90 capsules of 5 mg or 10 mg strength bardoxolone methyl. Each bottle will also contain a desiccant insert that must not be ingested. Labeling on each kit bottle will contain at minimum the following information:

- Medication identification number;
- Protocol 402-C-1602;
- Caution Statement: New Drug – Limited by Federal Law to Investigational Use. Keep out of sight and reach of children;
- Control or lot number
- Store at 20° - 25°C (68° - 77°F), short term excursions allowed to 15° - 30°C (59° - 86°F);
- Reata Pharmaceuticals, Inc., Irving, TX.

A double panel label will be presented on the treatment bottle containing this and other information as well. Additionally, labeling in the relevant local languages for investigational medicinal product for use and distribution in the EU shall adhere to current Eudralex, Volume 4 Annex 13 guidance and requirements.

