2. INTRODUCTION

The purpose of this statistical analysis plan (SAP) is to describe the planned analyses and data displays to be included in the Clinical Study Report (CSR) for Protocol 402-C-1602 (i.e., the RANGER trial).

Protocol Revision Chronology:		
Protocol Version 1	27-Oct-2016	Original
Amendment 1 (Protocol version 2)	05-Jan-2017	
 • Clinical study manager and contact information is updated. • Estimated study date is updated. • Study schema figure is updated. • Weight in clinic collection is added at Week 24 and End of Study Visit. • Number of dispensed kits are updated. • Week 4 visit is made uniform for all countries.
Amendment 2 (Protocol version 3)	16-Jul-2018	
 • Visit Schedule is revised with additional monitoring during first 8 weeks. • Dose-titration scheme is changed with increased dosing at week 4. • Dose Regiment is revised. • Clinical chemistries and local chemistry are added throughout study. • Additional monitoring for fluid status is included during first 8 weeks of treatment.

This SAP was developed in accordance with ICH E9 guideline. All decisions regarding final analysis, as defined in this SAP document, will be made prior to the initial Database Lock of the study data. Since the trial is an open-label study, analyses will be re-run based on subsequent database locks as needed for regulatory reporting and/or submissions so long as data continue to accrue. Further information can be found in the protocol.

The statistical analysis plan (SAP) is based on:

- Protocol No. 402-C-1602 Extension, Version 3, dated July 16, 2018
- ICH guidelines E4 and E9 (Statistical Principles for Clinical Trials)

This SAP describes the study populations, how variables are derived, how missing data are handled, and details concerning the statistical methods to be used to analyze the safety and efficacy data in the 402-C-1602 study. Should the SAP and the protocol be inconsistent with respect to the planned analyses, the language of the SAP is governing.

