6.6.4. Missing Treatment or Study End Date

The study was terminated on March 30, 2020. If the treatment end date or study end date are missing, the date will be imputed as March 30, 2020. If the treatment end date or study end date are missing and no reason for treatment or study discontinuation are included in the CRF, the reason for treatment or study discontinuation will be study termination.

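### SAP 9.2 divides compliance by capsules supplied, not capsules due, so it does not measure adherence: under the smallest supply, a perfect adherer who returns all surplus scores 57.0% to 85.6% at Week 24 and 77.8% to 90.7% at Week 72

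*SAP*

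**What the plan says.** SAP 9.2 (Exposure and Compliance) counts supply in whole bottles: "Total number of doses dispensed and total dose (mg) dispensed are calculated from total number of kits (bottles) recorded on the Study Drug Dispensation eCRF". Doses received are that total minus the doses returned. "Study drug compliance (%) is calculated as" 100 times received over dispensed. Protocol 9.4 (Treatment Compliance) gives no formula, and neither document defines doses due.

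Supply follows Protocol 9.10.10: "The patient will be dispensed 1 or more treatment kits at Day 1, Week 4, Week 24, and every 24 weeks thereafter", with each visit's kits to come back at the following visit. Protocol 10.2 itemises 10-mg capsules in one form only, "one 100-cc (10-mg capsules, 90 count) high-density polyethylene bottle". A later sentence there does not tie count to strength: "Each bottle of study drug will contain 30 or 90 capsules of 5 mg or 10 mg strength bardoxolone methyl".

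Two SAP rules bear on the last dose. Section 6.6.4 records that the study was terminated and says "If the treatment end date or study end date are missing, the date will be imputed as March 30, 2020". Section 9.2 says that, for patients still being treated at a data cut, "the last kit dispensed date is considered the date of last dose".

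**The concern.** With full returns, received over dispensed equals adherence only when supply equals doses due. Here it cannot: 14, 140 and 168 doses fall due in successive dispensing intervals, and none is a multiple of 30 or 90. Surplus handed out and properly returned is therefore scored as non-compliance. The size of the error depends on bottle size, kits per visit and where in an interval the patient stops.

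The last factor matters in this study. SAP version 2.0 is dated 5 June 2020, after the termination date of 30 March 2020. Patients on treatment then stopped wherever they stood in a 24-week supply cycle, with unused capsules in hand.

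At stake is the reading of the compliance summary. Scores are not comparable between patients with different times on study. Because results are shown by treatment analysis group, groups that differ in follow-up could differ in compliance at equal adherence.

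**Working it through.** Neither document states an expected compliance value or threshold, so there is no plan figure to reproduce.

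**Inputs from the documents**
- Regimen (Protocol 7.1 and 7.3.1): every other day to Week 4, then once daily. Doses due: 28/2 = 14 to Week 4; 20 × 7 = 140 from Week 4 to Week 24; 24 × 7 = 168 in each later interval.
- One capsule per dose (Protocol 9.10.9).
- Dispensing, returns and bottle sizes as described above. Returned kits do not carry over.
- This is the version 3 schedule. The SAP 2 chronology says of that amendment (16 July 2018): "Dose-titration scheme is changed with increased dosing at week 4". Patients who started earlier may have other counts.

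**Assumptions not in the documents**
- Perfect adherence and full returns.
- Treatment ends at the stated time, and kits handed out at that visit are not counted.
- Supply A: fewest 90-count bottles, giving 90, 180, 180, 180 capsules per dispensing.
- Supply B: fewest capsules if 30-count 10-mg bottles also exist, giving 30, 150, 180, 180.

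**Formula:** score = 100 × (sum of doses due) / (sum of capsules dispensed).

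| Treatment ends | Doses due | Supply A | Score A | Supply B | Score B |
|---|---|---|---|---|---|
| Week 24 | 14 + 140 = 154 | 270 | 57.0% | 180 | 85.6% |
| Week 36 (mid-interval) | 154 + 84 = 238 | 450 | 52.9% | 360 | 66.1% |
| Week 48 | 154 + 168 = 322 | 450 | 71.6% | 360 | 89.4% |
| Week 60 (mid-interval) | 322 + 84 = 406 | 630 | 64.4% | 540 | 75.2% |
| Week 72 | 322 + 168 = 490 | 630 | 77.8% | 540 | 90.7% |
| Day 624 (mid-interval) | 14 + 596 = 610 | 810 | 75.3% | 720 | 84.7% |

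Day 624 is the longest possible version 3 follow-up: 16 July 2018 to 30 March 2020 is 623 days.

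**Sensitivity**
- Kits handed out at the visit included (supply A): 154/450 = 34.2% at Week 24 and 490/810 = 60.5% at Week 72.
- Once daily from Day 1, as Protocol 9.10.9 could be read: 168/270 = 62.2% and 504/630 = 80.0% under A; 168/180 = 504/540 = 93.3% under B.
- Day 1 leftover kept, so that Week 4 needs one 90-count bottle: 154/180 = 85.6% and 490/540 = 90.7%, the same as B.

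**Comparability over time.** A patient ending at Week 72 matches a perfect adherer ending at Week 24 after taking only (154/270)/(490/630) = 73.3% of due doses under A, or (154/180)/(490/540) = 94.3% under B.

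**The opposite error.** Take a patient at Week 24 under A who took 80% of due doses, 0.8 × 154 = 123.2.
- Everything returned: 123.2/270 = 45.6%.
- Half the leftover returned: (270 − 0.5 × 146.8)/270 = 72.8%.
- Nothing returned, and the shortfall counted as received: 270/270 = 100%.

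**With doses due as denominator** and full returns, the perfect adherer scores 154/154 = 100% and the 80% adherer 123.2/154 = 80%. If nothing is returned, the new ratio would be 270/154 = 175.3%, so unreturned bottles need their own rule.

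**The case against.** The strongest reply is that little depends on this number. Compliance is not among the endpoints (Protocol 6.2, SAP 3.2.1). The safety population requires only one dose, there is no per-protocol set, and all analyses are descriptive. Exposure duration comes from dates, and total mg received is dispensed minus returned, so neither uses the faulty denominator. That stands and limits the severity.

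It is also fair that the percentages are scenarios. Bottles per visit are not stated, and SAP 9.2 produces one total per patient, so a Week 24 figure describes only someone whose treatment ends then. A reader might infer that the report will show about 57% or 78%; the documents do not support a prediction. They support only that no full-return case examined gives a perfect adherer 100%.

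A reader might also infer that patients who stop mid-interval score lowest by construction. They do not: the Day 624 stopper (75.3% under A) scores above patients who complete Week 24 (57.0%) or Week 48 (71.6%). The penalty is relative to finishing the same interval. Nor is the bias always downward, since unreturned capsules can push the score up. SAP 6.6.1, which rules out imputing missing data, might be read as leaving the score missing when a return is unrecorded, but SAP 9.2 does not say so.

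Finally, the two last-dose rules and the difference between Protocol 9.10.9 and 7.1/7.3.1 are not part of this defect, because no date or frequency enters the present formula. They matter only as inputs to a corrected denominator.

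**Conclusion.** Wrong as written, low impact. Applied exactly, SAP 9.2 reports the share of supplied capsules not returned under the name of compliance.

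With full returns, the modelled version 3 regimen, the smallest supply per dispensing and treatment ending before new kits are counted, a perfect adherer scores 57.0% (Week 24) and 77.8% (Week 72) with 90-count bottles. The figures are 85.6% and 90.7% if 30-count 10-mg bottles exist; Protocol 10.2 is ambiguous on that. Stopping at Week 36 gives 52.9% or 66.1%, against 71.6% or 89.4% for finishing that interval. If unreturned capsules count as received, the score reaches 100% at any true adherence. The direction for a given patient therefore depends on returns, and the documents do not allow the net effect to be predicted.

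**What to change.** Define compliance (%) as 100 × (capsules dispensed − capsules returned) / capsules expected under the regimen prescribed for that patient, summed over dispensing intervals with complete return counts.

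- Remove intervals with unreturned bottles from both numerator and denominator, and report how many were removed.
- Use recorded frequency and dose changes, and subtract recorded interruptions. Where these are not recorded, state the assumed schedule and note that unrecorded interruptions will count as missed doses.
- State whether SAP 6.6.4 or SAP 9.2 sets the last dose. If the SAP 9.2 rule applies at a cut, leave out kits dispensed on that date.
- Reconcile Protocol 9.10.9 with 7.1 and 7.3.1, so that the expected count is defined.

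The cost is SAP wording and one derivation. The numerator uses the dispensation and return forms already named in SAP 9.2, and Protocol 10.5 already requires returned capsules to be counted per bottle. The documents describe no form for dated frequency changes or interruptions, so an assumed schedule may be needed. Some intervals will become missing, and capsules lost from a bottle that was returned will still be credited as taken.

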**Table 3: Schedule of Assessments**

Assessment \ Study Week (Day)	Day 1 a	Week 1 (Phone) Day 3±2	Week 1 Day 7±3	Week 2 (Phone) Day 10±2	Week 2 Day 14±3	Week 3 (Phone) Day 21±2	Week 4 Day 28±3	Week 4 (Phone) Day 31±2	Week 5 (Phone) Day 38±2	Week 6 Day 42±3	Week 8 Day 56±3	Week 24±3, Every 24 Weeks	End of Study Visit b
Informed consent	X												
Inclusion/Exclusion	X												
Prior and Concomitant medications	X c	X	X	X	X	X	X	X	X	X	X	X	X
Current PAH background medications	X c	X	X	X	X	X	X	X	X	X	X	X	X
Weight at home	X	X	X	X	X	X	X	X	X	X	X		
Weight in clinic	X c		X		X		X			X	X	X	X
Vital sign measurements	X c		X		X		X			X	X	X	X
Physical examination	X c		X		X		X			X	X	X	X
Pregnancy test d	X c											X	
Dispense study drug	X						X					X	
Collect study drug							X					X	X
Telephone contact		X		X		X		X	X				
Adverse event collection	X c	X	X	X	X	X	X	X	X	X	X	X	X
Clinical Chemistries f	X c		X		X		X			X	X	X	X
BNP and/or NT-Pro BNP	X c		X		X		X			X	X	X	X
6-min walk test	X c											X	X
Dyspnea and fatigue g	X c											X	X
WHO functional class	X c											X	X

a On Day 1, all procedures should be performed before study drug administration for patients who are treatment-compliant and have previously participated in clinical studies with bardoxolone methyl.

b After the Week 24 visit, patients will continue to be assessed in person every 24 weeks. The End of Study visit should occur within 30 days after the patient receives their final dose of study medication under this protocol. Patients who will be discontinued from the study prior to the completion of the study must also complete all End-of-Study assessments.

c Day 1 assessments should be performed as part of End-of-Treatment or Follow-up visit procedures from a prior study with bardoxolone methyl.

d A serum pregnancy test will be performed at any point in time if a pregnancy is suspected. All other pregnancy assessments will be urine pregnancy tests. Additional pregnancy assessments will be performed more frequently if required by local law or requested by local health authorities or IRBs/ECs.

e AE assessments on Day 1 should be performed following study drug administration.

f Clinical chemistries will be analyzed locally.

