6.6.3. Missing Start and Stop Dates for Adverse Events

Treatment-emergent adverse events (TEAEs) are events that either:

- Had a date of onset on or after the date of the date of first dose of study drug and not more than 30 days after the date of the last dose of study drug, or
- Had no recorded date of onset with a stop date after the first dose of study drug, or
- Had no recorded date of onset or stop date.

Adverse events with incomplete start dates are considered after the date of first dose if:

- Day and month are missing, and the year is equal to or after the year of the first date of study drug administration;
- Day is missing and the year is after the year of the first date of study drug administration;
- Day is missing and the year is equal to the year of the first date of study drug administration and the month is equal to or after the month of the first date of study drug administration; or
- Year is missing.

Adverse events with incomplete start dates are considered on or within 30 days of last dose, if:

- Day and month are missing, and the year is equal to or before the year of the date of last dose of study drug plus 30 days;
- Day is missing and the year is equal to or before the year of the date of last dose of study drug plus 30 days, and month is equal to or before the month of the date of last dose of study drug plus 30 days;
- Year is missing.

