9.1. Adverse Event Preferred Term and Body/Organ System Summary Tables

AEs are summarized by treatment analysis group as defined by the safety analysis set. General considerations for AE summaries and calculations are:

- Multiple events by preferred term (PT) and system organ class (SOC) are counted once only per patient for each treatment analysis group.
- For summaries by severity, only the most severe event is counted per patient for each treatment analysis group.
- For summaries by relationship, for frequency counts by patient, only the most related event is counted per patient for each treatment analysis group.
- An AE with a missing resolution date or incomplete date that is not identified as continuing is assumed to be continuing and no duration is calculated.
- Only treatment-emergent adverse events (TEAEs) are included in summaries.

AEs are coded using MedDRA (Medical Dictionary for Regulatory Activities) version 19.0. In MedDRA, each verbatim term is mapped to a preferred term and high level term (HLT), which is then mapped to a system organ class. Tables and listings present data at the SOC and PT level.

Treatment-emergent adverse events (TEAEs) are events that either:

- Had a date of onset on or after the date of the date of first dose in the RANGER study and not more than 30 days after the date of the last dose of study drug in the RANGER study, or
- Had no recorded date of onset with a stop date after the first dose of study drug, or
- Had no recorded date of onset or stop date.

Adverse events with a date of onset in LARIAT or CATALYST that continued during the RANGER study are not considered TEAEs.

In addition, adverse events which occurred >30 days after the date of last dose of study drug are listed as late-onset AEs (LOAEs). These are adverse events that had a date of onset more than 30 day after the date of the last dose of study drug.

The investigator grades the severity of the AEs as mild, moderate, or severe as defined in the study protocol Section 11.5.

Association or relatedness to the study medication are graded by the investigator according to criteria specified in Section 11.4 of the study protocol.

As defined in the protocol and captured on the CRF, a serious adverse event (SAE) is an adverse event that results in any of the following:

- Death;
- A life-threatening adverse drug experience;
- Inpatient hospitalization or prolongation of existing hospitalization;

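### SAP 9.2 dates the last dose of patients still on treatment at a data cut to their last kit dispensing, which understates exposure and, read literally, closes the TEAE window while they are still dosing

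*SAP*

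**What the plan says.** SAP 9.2 defines exposure as last dose minus first dose plus 1. For patients still being treated at an interim or final cut it adds that "the last kit dispensed date is considered the date of last dose".

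Protocol 9.10.10 sets the dispensing schedule: "The patient will be dispensed 1 or more treatment kits at Day 1, Week 4, Week 24, and every 24 weeks thereafter".

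SAP 9.1 counts an event with a recorded onset as treatment-emergent if it starts on or after the first RANGER dose and "not more than 30 days after the date of the last dose of study drug in the RANGER study". SAP 6.6.3 has the same limit. SAP 9.1 also states: "Only treatment-emergent adverse events (TEAEs) are included in summaries". Events starting later are listed as late-onset AEs.

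SAP 5.1 requires every planned output at each interim analysis, and SAP 2 allows re-runs at later locks while data accrue. SAP 5.2 places the final analysis after the last patient has completed. SAP 6.6.4 records termination on 30 March 2020 and imputes that date where a treatment or study end date is missing.

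**The concern.** A dispensing date is about the earliest day on which a kit can be used. Taking it as the last dose removes all dosing from that kit from the exposure duration. SAP 9.2 is also at odds with itself: doses received are doses dispensed minus doses returned, so an unreturned last kit counts as fully received although exposure ends on the day it was handed over.

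The larger stake is the adverse event tables. AE and SAE frequency is part of the primary safety endpoint (Protocol 6.2, SAP 3.2.1). The TEAE definition depends on the date of last dose, SAP 9.2 supplies that date for ongoing patients, and nothing confines it to the exposure calculation. A programmer who derives one last-dose variable and uses it throughout would move recent on-treatment events out of the tables. The error runs one way: exposure shrinks, and events with a known onset can only leave the tables.

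**Working it through.** The documents give no exposure total or TEAE count to reproduce, so the check is date arithmetic.

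**Inputs**
- Kit days 1, 28, 168 and 336, from Protocol 9.10.10. Weeks times 7 gives the target days in SAP Table 3 (Week 4 = 28, Week 24 = 168, Week 48 = 336).
- Exposure = last dose - first dose + 1 (SAP 9.2).
- End of TEAE window = last dose + 30 days (SAP 6.6.3 and 9.1).
- Assumptions: visits fall on the nominal day, the patient doses up to the cut, and the cut precedes the next dispensing.

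**Formulas**
- Exposure lost = cut day - kit day.
- On-treatment days outside the TEAE window = max(0, cut day - kit day - 30).

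| Last kit | Cut falls on | Most exposure lost | Most days outside TEAE window |
|---|---|---|---|
| Day 1 | Day 1 to 27 | 27 - 1 = 26 | 0 |
| Day 28 | Day 28 to 167 | 167 - 28 = 139 | 139 - 30 = 109 |
| Day 168 (later cycles alike) | Day 168 to 335 | 335 - 168 = 167 | 167 - 30 = 137 |

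**Averages**, assuming the cut is equally likely on any day of the interval:
- After the Week 4 kit: mean exposure lost 139/2 = 69.5 days; some TEAE time lost on 109/140 = 78% of cut days; mean TEAE time lost (109 × 110/2)/140 = 42.8 days.
- Later cycles: 167/2 = 83.5 days; 137/168 = 82%; (137 × 138/2)/168 = 56.3 days.

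These are days of window, not events.

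**Visit window.** The unit of the ±3 on Week 24 in the schedule is not given. If days, the gap between kits can reach 168 + 6 = 174 days and the maxima become 173 and 143. If weeks, the gap can reach 168 + 42 = 210 days and the maxima become 209 and 179.

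**Example.** First dose Day 1, last kit Day 168, interim cut Day 250. Exposure is 168 days under SAP 9.2 and 250 days to the cut, so 82 days are lost. The TEAE window closes on Day 168 + 30 = 198. A first SAE of a given term on Day 220, while dosing, is 220 - 168 = 52 days after the assigned last dose, so on the literal reading it is listed but is not in the SAE table.

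**Final lock.** SAP version 2.0 is dated 05 June 2020, 67 days after termination on 30 March 2020. As an illustration, take a patient with no recorded end date and a last kit on 01 January 2020. SAP 9.2 would give 01 January and SAP 6.6.4 would give 30 March, which is 30 + 29 + 30 = 89 days apart.

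**The case against.** **The scenario may not arise.** Treatment had ended before this SAP version was dated. Protocol 7.4 stops all study drug when the sponsor ends the study, re-runs are tied to accruing data, and no interim cut with ongoing patients is documented as pending. This stands. A reader might infer that the final tables are missing events; the documents do not support that. The number of patients affected cannot be derived and may be zero.

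**The TEAE effect is inferred.** The sentence sits in the exposure section, 9.2 does not mention TEAEs, and neither 9.1 nor 6.6.3 refers to 9.2. This also stands. The SAP does not say that the kit date closes the TEAE window. It uses one term in all three places and gives no second definition, so the reading is open, not required. The exposure shortfall needs no such inference.

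**SAP 9.2 and 6.6.4 need not collide.** Section 9.2 covers patients still on treatment. Section 6.6.4 covers missing end dates after termination and, where no reason is recorded, assigns study termination as the reason. A patient so classified is no longer on treatment. It would therefore go too far to call the two rules contradictory for everyone. They overlap only if a patient with no recorded end date is taken as still on treatment. Because 9.2 still names a final cut, that remains possible, and no precedence is stated.

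**The reach is limited even at an interim cut.** Patients who died or discontinued before the cut are not covered by the rule, so one should not infer that deaths or AEs leading to discontinuation are generally dropped. Events with a missing onset date, and some with partial dates, can still qualify as TEAEs. SAP 5.1 calls interim results preliminary, and all AEs stay in the listings. The counting rule, "Multiple events by preferred term (PT) and system organ class (SOC) are counted once only per patient for each treatment analysis group", means that a table changes only if the excluded days bring a new term, or a more severe or more related event.

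**Conclusion.** The rule is wrong as written for any cut with patients still dosing. Its effect on exposure is certain there: up to 139 days per patient after the Week 4 kit and up to 167 days after later kits, on the nominal schedule. Its effect on the AE tables, up to 109 or 137 days of dosing outside the TEAE window, depends on applying the 9.2 date to the definitions in 6.6.3 and 9.1. The wording permits this but does not state it.

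At the final lock, the remaining issue is narrow: a patient with no recorded end date could be handled by 9.2 or by 6.6.4, with different results. The point is worth correcting because the SAP keeps the sentence for both kinds of cut and the repair is small, not because the documents show that any reported result has been distorted.

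**What to change.** 1. Delete the last-kit sentence from SAP 9.2.
2. At any cut with patients still on treatment, end their exposure at the data-cut date and count every AE with onset from first dose through the cut as treatment-emergent.
3. At the final analysis, state that 6.6.4 governs missing treatment end dates: 30 March 2020, or the date of death if earlier. Use that date as the date of last dose for both exposure and TEAEs, and say explicitly that the 30-day extension of the TEAE window after it is kept.

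Do not cap at the last scheduled contact instead. Protocol Table 3 says: "After the Week 24 visit, patients will continue to be assessed in person every 24 weeks". Those visits are also the dispensing visits, so from Week 24 the cap can restore the last-kit date. Between Week 8 and Week 24 it would stop at about Day 56.

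The work is about two SAP sentences and one derivation in the exposure dataset. The drawback is that exposure is overstated for a patient who stopped without a report. On the nominal schedule this can reach about one dispensing interval, 167 days, if the patient stopped just after a 24-weekly dispensing, so it should be disclosed alongside the exposure summary.
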